#### **7.3.5.1 Pregnancies**

Any subject who becomes pregnant during the course of treatment will be instructed to immediately stop all treatments and will be discontinued from the study. Also, any subject who becomes pregnant in the two week period following their completion of the treatment phase of the study, or their discontinuation from the study (for reasons other than pregnancy), will be instructed to contact the clinic to report the pregnancy. All treated study subjects who report a pregnancy during the course of the trial will be followed during the course of their pregnancy by the study doctor to determine the outcome of the pregnancy.

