Once the SAE form is complete, the Medical Monitor will forward it, by email, to the Vice President of Clinical Research at Topical Remedy (email: [contact]; [contact]) for review. The Vice President of Clinical Research will send any comments to Drug Safety. Drug Safety will track the SAE information and forward a desk copy of the complete SAE report to Topical Remedy, LLC.

Adverse events, whether serious or non-serious, will be followed to resolution or until the condition stabilizes, is otherwise explained, or the subject is lost to follow-up, up to a maximum of 30 days following the subject's last clinic visit. Adverse events, whether serious or non-serious, will be captured up to 2 weeks following the last clinic visit, and followed up to a maximum of 30 days following the subject's last clinic visit. Where appropriate, medical tests and examinations will be performed to document resolution of event(s). Outcome may be classified as resolved, improved, unchanged, worse, fatal, or unknown (lost to follow-up). Following the resolution of any study associated adverse events or after the completion of the Treatment Phase of the study, there will be no further adverse event reports for that subject.

While pregnancy itself is not considered to be an AE, any pregnancy complication or elective termination of a pregnancy for medical reasons will be recorded as an AE or SAE (as appropriate). A spontaneous abortion is always considered to be a SAE.

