## 7.9 Pregnancy

A listing of vital signs will be provided for the Safety Population.

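### The adverse event time limits in Protocol Section 8 make no exception for the pregnancy outcomes the protocol wants followed and recorded, and SAP 7.9 (Pregnancy) lists vital signs instead.

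*Protocol*

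**What the plan says.** Two sets of protocol rules bear on a pregnancy in a treated subject.

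**Duty to follow and record.** Section 7.3.5.1 says that treated subjects who report a pregnancy "will be followed during the course of their pregnancy by the study doctor to determine the outcome of the pregnancy". It also asks "any subject who becomes pregnant in the two week period following their completion of the treatment phase of the study", or following discontinuation for another reason, to report it to the clinic. Section 8 says that pregnancy is not itself an AE, but that complications and terminations for medical reasons are recorded as AEs or SAEs. It adds: "A spontaneous abortion is always considered to be a SAE". Its definition of a serious event includes a congenital anomaly or birth defect.

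**Limits on recording.** Section 8 also states that adverse events, serious or not, "will be captured up to 2 weeks following the last clinic visit, and followed up to a maximum of 30 days" after that visit. The same paragraph ends by saying that following resolution of study-associated events, or "after the completion of the Treatment Phase of the study, there will be no further adverse event reports for that subject".

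**SAP.** Section 7.9, headed Pregnancy, reads in full: "A listing of vital signs will be provided for the Safety Population". Section 7.8, Vital Signs, has the same sentence. No table in SAP Section 10 is for pregnancy.

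**The concern.** The limits in Section 8 are written for all AEs, serious or not, and none of them excepts pregnancy. Most pregnancy outcomes come long after a cold-sore episode has healed. A site that reads Section 8 literally has a duty to find the outcome, a duty to record some outcomes as AEs or SAEs, and a rule that has already closed the record.

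The SAP does not fill the gap. An uncomplicated pregnancy after exposure is not an AE, so no TEAE table can show it. The section where one would look for it lists other data.

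What is at stake is the completeness of safety reporting on a risk that the protocol singles out through its contraception requirement, screening test, exclusion criteria and outcome follow-up.

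**Working it through.** The plan gives no figure of its own to reproduce. The check is date arithmetic plus a comparison of the rules.

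**Inputs**
- Treatment Day is Day 0.
- Clinic visits end between Visit Day 3 and Visit Day 14 (Protocol 7.3 and 7.3.1). Visit Day 1 may fall on Treatment Day or the day after (Table 7-1, footnotes 4 and 7). The last clinic visit, L, is therefore about Day 2 to Day 14 for a subject who completes.
- Capture closes at L + 14 and follow-up at L + 30 (Protocol Section 8).
- Subjects are asked to report pregnancies that begin up to 2 weeks after the Treatment Phase (Protocol 7.3.5.1), so to about Day 14 + 14 = Day 28.
- The safety call is 2 weeks, or up to 3, after the Treatment Phase (Protocol 7.4), so by about Day 14 + 21 = Day 35.

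**When the limits close**
- Capture: 2 + 14 = Day 16, to 14 + 14 = Day 28.
- Follow-up: 2 + 30 = Day 32, to 14 + 30 = Day 44.
- End-of-Treatment-Phase sentence: Protocol 7.4 puts completion at healing or Visit Day 14, so Day 14 at the latest. This is earlier than the 2-week capture limit in the same paragraph.

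**Room left after conception**, for conception on Day c, from 0 to L + 14
- Until capture closes: L + 14 − c. The most is 14 + 14 − 0 = 28 days. The least, at c = L + 14, is 0 days.
- Until follow-up closes: L + 30 − c. The most is 14 + 30 − 0 = 44 days. The least, at c = L + 14, is 16 days.

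So an outcome more than 28 days after conception falls outside capture, and one more than 44 days after falls outside both limits. This needs no assumption about the length of pregnancy. A pregnancy already present but unrecognised at first application would have somewhat more of its course inside the limits.

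**Illustration.** The documents give no length of pregnancy. Assuming about 266 days from conception to term, conception between Day 0 and Day 28 gives a birth at about Day 266 to 294. That is 266 − 44 = 222 to 294 − 44 = 250 days after the latest follow-up limit.

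**Where each kind of information would go as written**
- Event inside the capture window: recorded as an AE or SAE, then in the TEAE tables. SAP 7.12 defines a TEAE by its start on or after first dose, with no upper limit.
- Complication, medical termination, spontaneous abortion or birth defect after the limits: to be determined under 7.3.5.1, with no stated place to record it.
- Uncomplicated pregnancy and live birth: not an AE, and no listing specified.
- Screening pregnancy test and Treatment Day pregnancy status: collected (Table 7-1), but no listing specified.

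**The case against.** A reader might infer that pregnancy outcomes would be neither captured nor reported, that exposed pregnancies would leave no trace, or that nearly all outcome SAEs would be missed. The documents do not support this.

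- Section 7.3.5.1 requires outcomes to be determined.
- Early losses or complications fall inside the capture window.
- The pregnancy rule in Section 8 is a separate paragraph with no time limit of its own, and a sensible site could read it as overriding the general limits. All SAEs go to the Drug Safety Group within 24 hours.
- Any event recorded enters the TEAE tables, and the serious TEAE table if serious.
- A subject who becomes pregnant during treatment is discontinued, and SAP 7.3 summarises early terminations with reasons.

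These points stand, and they remove the stronger claims. They do not remove the conflict. Section 8 applies its limits to serious events expressly and says that reports cease, so the sensible reading has to be supplied by the site. The tabulation and SAE routes both depend on the event first being recorded.

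A reader might also infer that 7.3.5.1 excludes pregnancies reported after the Treatment Phase, because it follows those reported while the trial is in progress. That is an ambiguity, not an exclusion. The preceding sentence asks for reports of pregnancies that begin in the next 2 weeks, and the trial as a whole runs for about 9 months.

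Finally, tests and Treatment Day status will be almost uniformly negative in treated subjects, because a positive answer excludes them, and the SAP 7.9 sentence looks like a copying error. Both points are fair. The main content of the listing should be reported pregnancies and their outcomes.

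**Conclusion.** The concern holds as an unreconciled conflict between stated rules together with a wrong SAP output. Section 7.3.5.1 and the pregnancy paragraph of Section 8 require outcomes to be found and some of them recorded. The general limits in Section 8 close the record by about Day 28 for capture and Day 44 for follow-up at the latest, without exception. SAP 7.9 specifies no pregnancy listing, which leaves uncomplicated exposed pregnancies with no dedicated output.

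The practical size is small. The documents give no expected number of pregnancies. An assumed 0 to 2 among about 150 treated subjects is plausible given the contraception requirement. Sample size, Type I error and efficacy analyses are untouched. The correction is still worth making, because the protocol has already committed to obtaining these outcomes and the change costs very little.

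**What to change.** 1. **Protocol Section 8.** Reconcile it with 7.3.5.1 by stating that the 2-week capture limit, the 30-day follow-up limit and the end of reporting after the Treatment Phase do not apply to outcomes of pregnancies followed under 7.3.5.1.
2. **Protocol 7.3.5.1.** Clarify that the pregnancies followed to outcome include those beginning in the 2 weeks after completion or discontinuation, which the preceding sentence already asks subjects to report.
3. **SAP 7.9.** Replace the vital-signs sentence with a Safety Population listing of reported pregnancies and their outcomes, with the pregnancy test and Treatment Day pregnancy status as already collected.

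The cost is a few sentences and one listing. Follow-up by the study doctor is already planned. If a site had read 7.3.5.1 narrowly, item 2 could add follow-up of an occasional pregnancy. A rare outcome may arrive after database lock and need an addendum to the study report.

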 The follow-up (F/U) study visit for safety is to be conducted by telephone 2 weeks, or up to 3 weeks, if there are scheduling issues, after the subject completes the Treatment Phase of the study

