### **7.4 Follow-Up Telephone Assessment**

Two weeks, or up to 3 weeks, if there are scheduling issues, after the subject has completed the Treatment Phase of the study (complete healing of the herpetic episode or Visit Day 14, whichever is earlier) the clinic will contact the subject by phone for a final safety evaluation. Any new adverse events that have occurred since the subject's last clinic visit should be collected at this time.

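### Protocol Section 8 ends adverse event reporting with the Treatment Phase, contradicting its own 2-week capture window and the Section 7.4 safety call

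*Protocol*

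**What the plan says.** The follow-up and outcome paragraph of Protocol Section 8 states that adverse events, serious or not, "will be captured up to 2 weeks following the last clinic visit, and followed up to a maximum of 30 days", both counted from the subject's final visit. The last sentence of that paragraph gives two triggers for ending reports. One is resolution of a study-associated event. The other is the end of the phase: "after the completion of the Treatment Phase of the study, there will be no further adverse event reports for that subject".

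Section 7.4 says when that phase ends: "complete healing of the herpetic episode or Visit Day 14, whichever is earlier". It times the safety call from there: "Two weeks, or up to 3 weeks, if there are scheduling issues, after the subject has completed the Treatment Phase of the study". Its purpose is explicit, since new events arising after the subject's "last clinic visit should be collected at this time". Footnote 11 to Table 7-1 says the same of the follow-up contact, which "is to be conducted by telephone 2 weeks, or up to 3 weeks" after the phase; SAP Section 5 repeats the footnote.

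Two further statements bear on the window. The opening sentence of Section 8 asks for case report form (CRF) recording of events that occur during the Treatment Phase, while a later sentence in the same paragraph records events after application of study treatment and gives no end date. SAP 7.12 defines treatment-emergent events from the first dose, also with no end date.

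The protocol synopsis and SAP 6.2 both make adverse events the only safety endpoint.

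**The concern.** The closing sentence of Section 8, if applied, bars the very reports that the safety call exists to collect. It makes no exception for serious events, although the capture sentence covers serious and non-serious events alike. Nor does it exempt pregnancy complications, although Section 7.3.5.1 asks subjects to report pregnancies arising in the two weeks after the phase and Section 8 records complications as adverse events.

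With about 5 to 10 centers planned, one site may enter events from the call while another, or a data manager, closes the subject at healing. The adverse event tables would then partly reflect site practice. The SAP cannot settle the matter, because its definition of a treatment-emergent event has a start and no end.

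**Working it through.** No figure in the plan needs reproducing. The check sets the passages side by side and counts days.

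**Step 1. Common time point.** Let T be completion of the Treatment Phase. Protocol 7.4 puts T at healing or Visit Day 14, whichever is earlier. Under Section 7.3, clinic visits end at Stage 7 or Visit Day 14, but not before Visit Day 3. For a subject who heals on Visit Day 3 or later, T is therefore the last clinic visit, and T lies between Visit Day 3 and Visit Day 14. A subject who heals before Visit Day 3 still attends until then, so the closing sentence would stop reports even before the last visit.

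**Step 2. Days of new-event capture after T.**

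| Rule | Days after T | Ends if T = Day 3 | Ends if T = Day 14 |
|---|---|---|---|
| Section 8, closing sentence | 0 | 3 + 0 = Day 3 | 14 + 0 = Day 14 |
| Section 8, capture sentence | 14 | 3 + 14 = Day 17 | 14 + 14 = Day 28 |
| Section 7.4, safety call | 14 to 21 | 3 + 14 = Day 17 to 3 + 21 = Day 24 | 14 + 14 = Day 28 to 14 + 21 = Day 35 |

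The 30-day limit in Section 8 concerns following known events to outcome, so it does not set a window for new ones.

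**Step 3. Can the rules be met together?** The whole 14-day capture window and the call itself fall after T, where the closing sentence allows nothing. They would agree only if the Treatment Phase included the call. Section 7.4 excludes that by timing the call from the end of the phase, and Section 7.3 says the phase could last as many as 14 days.

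The capture sentence and the call also differ from each other when the call is late: 21 - 14 = 7 days.

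**Step 4. Is the period after T empty of interest?** Protocol 5.4.4 asks subjects to limit sun exposure during use and for one week afterwards. As an illustration with assumed timing, take a last application at 96 hours (about Day 4) and healing on Day 5. The week runs to about Day 4 + 7 = Day 11, which is 11 - 5 = 6 days after the closing sentence would have ended reports.

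**The case against.** The strongest reply is that one badly worded sentence will not override several specific instructions. Section 7.3.5 has subjects questioned at every clinic visit and asked to report events at any time during the study. Section 7.4 tells sites what to collect on the call. Section 8 itself gives the 2-week window. The closing sentence may be no more than a clumsy attempt to say when a case is closed. This stands in part: a reader might infer that late events would certainly be lost, and the documents do not support that. Loss depends on someone applying the closing sentence.

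Three other stronger inferences also fail.

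- Read literally, the resolution trigger would end all reporting for a subject whose mild reaction cleared on Day 0. That runs against the questioning at each visit, the adverse event marks on every visit day in Table 7-1, and the rules in Protocol 10.6 and SAP 7.12 for events reported more than once.
- The adverse event row has no mark in the follow-up column of either schedule table. As the tables read, no row has one, and footnote 11 describes that contact as being for safety.
- A 3-week call might suggest that 7 of 21 days, a third, is lost. That is calendar time rather than events. It applies only to a call delayed for scheduling reasons, and Section 7.4 has no 14-day cut-off.

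The likely effect on the comparison is also limited. Allocation follows a sequence within each site and is blinded, so differences in recording should fall on both arms. SAP 7.1.1 and 7.2 plan no inferential testing of safety, and SAP 7.12 counts a subject once per event, so unrecorded repeats would seldom change an incidence. What none of this answers is that absolute event rates would still depend on which sentence a site followed.

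**Conclusion.** The point holds as an internal contradiction, not as a disputable design choice. Section 8 conflicts with itself and with Section 7.4, and the definition of Treatment Phase completion leaves no reading that reconciles them. Its size is the range of capture after the phase ends: 0, 14, or 14 to 21 days. Events in the only safety endpoint could be lost or recorded differently between sites. How many cannot be estimated, since the documents give no rate of late events and no indication of which rule sites would follow. The conclusion rests on the current wording alone. It should be corrected, but it does not touch the efficacy analyses or the sample size.

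**What to change.** - Delete or rewrite the Section 8 sentence that begins "Following the resolution of any study associated adverse events or after the completion of the Treatment Phase of the study".
- Amend the opening sentence of Section 8 so that CRF recording is not confined to the Treatment Phase; otherwise a second restrictive statement survives.
- State one end of the capture window for new events, in the same terms in Sections 7.4 and 8. It should cover the safety call, including a call made at 3 weeks, and give a fixed end date for subjects whose call is not made. Keep the 30-day limit as a separate rule for following known events to outcome.
- Check the two-week pregnancy-reporting period in Section 7.3.5.1 against that window.
- Add the same window to the treatment-emergent definition in SAP 7.12, so that the tables count what the sites were told to collect.

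The cost is protocol and SAP wording and perhaps a few more adverse event records. No visit or procedure is added, because the call is already planned.

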## 9 REMOVAL OF SUBJECTS FROM STUDY

Subjects will be advised that they are free to withdraw from the study at any time without consequence. The Investigator may remove a subject if he/she feels this action is in the best interest of the subject. When a subject withdraws from the study after treatment, all of the necessary safety and tolerability assessments should be obtained if possible.

Subjects experiencing adverse events should be followed until the event has resolved or until the condition stabilizes, is otherwise explained, or the subject is lost to follow-up, up to a maximum of 30 days following the subject's last study visit. Appropriate supportive and/or definitive therapy will be administered as required. As with other subjects in this study, compensation will be offered for return of a used or unused study kit.

Subjects withdrawn from this study cannot re-enter or be used as replacements for other subjects in this study.

## 10 STATISTICAL METHODS

### 10.1 Introduction

This trial will be conducted to test the superiority of the Merlin solution to placebo solution in the treatment of recurrent herpes labialis at first visible signs and/or symptoms of a herpetic lesion. The primary efficacy endpoint for the study will be the clinician assessed duration of the classical herpetic lesion. The duration of a classical lesion is defined as the time, in hours, from the beginning of treatment to the onset of Stage 6, or, if Stage 6 is never observed, Stage 7. A classical lesion is defined as one that progresses through any of the vesicle/pustule, ulcer, or crust stages (stages 3, 4 or 5). Duration of the classical herpetic lesion will be analyzed using the Hodges-Lehmann method as the primary efficacy analysis method for estimating the median difference between the two arms. Duration of the herpetic episode, duration of complete healing of the herpetic episode, duration of the herpetic lesion, duration of the herpetic lesion hard scab, and duration of pain will be analyzed in the same manner as the duration of the classical lesion.

### 10.2 Study Endpoints

#### 10.2.1 Efficacy Endpoints

##### Primary:

- Clinician assessed duration of the classical herpetic lesions

##### Secondary:

- Clinician assessed duration until of the herpetic episode
- Clinician assessed duration of until complete healing of the herpetic episode
- Clinician assessed prevention of progression to a classical lesion

- Maximum clinician assessed lesion size
- Clinician assessed duration of the herpetic lesion hard scab
- Clinician assessed duration and severity of lesion associated pain

Other Endpoints:

- Subject assessed duration and severity of lesion pain
- Subject assessed duration of the classical herpetic lesion
- Subject assessed duration of the herpetic episode
- Subject assessed duration of complete healing of the herpetic episode
- Subject assessed prevention of progression to a classical lesion
- Subject assessed duration of the herpetic lesion hard scab

### 10.2.2 Safety Endpoints

- Adverse events (AEs)

## 10.3 Study Populations

### 10.3.1 Safety Population

All subjects who have been entered into the Treatment Phase of the study and self-administered any treatment will be included in the safety population. A subject will be included in a treatment group for analysis based upon the treatment actually administered, rather than the group to which he or she has been assigned. For example, a subject who is randomized to receive placebo treatments but inadvertently receives active treatment will be included in the group receiving active treatment.

Should a subject gain access to their clinical trial materials and treat themselves without having called in to the clinic and been given permission to open their Treatment kit, that subject will also be included in the safety population if follow-up safety data are available.

### 10.3.2 Efficacy: Modified Intent-to-Treat (MITT) Population

All subjects who have been entered into the Treatment Phase of the study will be included in the MITT population. It is considered a “modified” intent to treat population in that it does not include all randomized subjects but includes only those randomized subjects who access their treatment, i.e., are told to open their kit. The MITT population will be used as the primary analysis population. A subject will be included in a treatment group for analysis based upon the treatment to which he or she has been assigned.

